#### 5. ELIGIBILITY

#### 5.1 Inclusion criteria

a) Age at diagnosis at least 4 years or 5 years (according to the policy of the National Brain Tumour Group) and less than 22 years.

The date of diagnosis is the date on which surgery is undertaken.

- b) Histologically proven medulloblastoma, including the following variants (WHO classification -2000):
  - classic medulloblastoma
  - nodular / desmoplastic medulloblastoma
  - melanotic medulloblastoma
  - medullomyoblastoma

Studies of large cell medulloblastoma indicate that this variant is associated with an aggressive biological behaviour and that it constitutes an independent risk factor for a poor prognosis. Consequently, patients withthe large cell variant of medulloblastoma are ineligible for entry into HIT-SIOP PNET 4. Large cell medulloblastomas are clearly defined in the WHO classification of CNS tumours, making up ~5 % of medulloblastomas. However, central pathology review is required before excluding patients with this variant from the trial (see Appendix D). The PNET 4 National Co-ordinator (Dr [name]) or the Chair of the UKCCSG PNET Group (Dr [name]) should be contacted for advice with regard to treatment of this tumour sub-type.

Although not required before study entry and randomisation, central pathology review of other variants is considered mandatory (see Appendix D).

c) No CNS metastasis on MRI – (supratentorial, arachnoid of the posterior fossa or spine)

It is recommended that MRI scan of the head and spine be performed before surgery. HIT-SIOP PNET 4 Protocol Version 3.0,  $27^{th}$  July 2010 (RG\_10-034)

If spinal axis imaging has not been performed before surgery, it should be performed before lumbar puncture in order to avoid artefacts (if positive in such circumstances, spine MRI should be repeated).

Although pre-operative MRI is recommended, a patient is eligible for randomisation/study entry if a CT scan of the head and not MRI is performed pre-operatively - provided an MRI of the head is performed post-operatively to exclude intracranial metastases and this scan is unequivocally negative. Prerandomisation neuroradiological imaging review for the head and spine is strongly suggested but not mandatory. It will be left to national policy.

- d) No clinical evidence of extra-CNS metastasis
- e) No tumour cells on the cytospin of lumbar CSF. Central Review of CSF cytology is recommended but not mandatory. It will be left to national policy.

Lumbar puncture should generally be performed at least 15 days following surgery, and before randomisation. If a lumbar puncture is performed before 15 days and is negative for tumour cells than this will be taken as evidence of non-metastatic disease. If, however, the CSF is positive by lumbar puncture before 15 days then the lumbar puncture must be repeated at 15 days or beyond to determine M1 status.

Involvement of CSF pathways by tumour is defined as the unequivocal identification of primitive neuroectodermal cells, either on cytological grounds or with a combination of cytological and immunohistochemical features (e.g. reactivity for GFAP or a neuronal marker, such as synaptophysin).

- f) Intention to start radiotherapy no more than 40 days after surgery. (patients will not be removed from study if radiotherapy starts after 40 days post surgery)
- g) Ability to receive twice daily radiotherapy.
- h) Vital functions within normal range for their age group.
- i) CTC grades < 2 for liver, renal, haematological and audiological function.
- j) No medical contraindication to radiotherapy or chemotherapy.
- k) Written informed consent (and patient assent where appropriate) according to the laws of each participating country. Written informed consent should also be sought for biological studies.
- 1) National and local ethical committee approval according to the laws of each participating country (to include approval for biological studies).

Patients with residual disease of any size following surgery are eligible for inclusion into the trial (section 4.2.2). The Study Committee do, however, suggest that second look surgery be considered in patients with significant residual disease following primary surgery.

#### 5.2 Exclusion criteria

- a) One of the inclusion criteria is lacking
- b) Brainstem or supratentorial primitive neuroectodermal tumour.
- c) Large cell medulloblastoma
- d) Atypical teratoid rhabdoid tumour.
- e) Medulloepithelioma.
- f) Ependymoblastoma
- g) Metastatic medulloblastoma (on CNS MRI and/or positive cytospin of postoperative lumbar CSF)
- h) Patient previously treated for a brain tumour or any type of malignant disease.
- i) Patients who are pregnant.
- j) Females who are sexually active and not taking reliable contraception.
- k) Known predisposition to medulloblastoma e.g. Gorlin's syndrome.

#### 6. DIAGNOSTIC STAGING AND INITIAL INVESTIGATIONS

## 6.1 Preoperative period

- a) Clinical examination with full neurological examination.
- b) Whole brain imaging MRI of brain pre and post contrast is strongly recommended in preference to CT scan with contrast.
  - 3D tumour measurements should be undertaken.
- c) MRI of the spine with visualisation of the end of the dural sac.

## **6.2 Post operative period** (see appendix G)

a) Cerebral MRI pre and post contrast injection.

Performed within 72 hours after surgery – Ideally between 24 and 48 hours of surgery

Postoperative scanning with MRI of brain, pre- and post-contrast, is strongly recommended in preference to CT scan with contrast, although cerebral CT scan without and with contrast injection is acceptable for local staging. The CT should be performed within 72 hours after surgery.

The size of any post operative residual tumour will be recorded.

- b) MRI of the craniospinal axis with visualisation of the end of the dural sac. (if not performed preoperatively)
- c) Lumbar puncture for CSF cytology.

Lumbar puncture should generally be performed at least 15 days following surgery, and before randomisation. If a lumbar puncture is performed before 15 days and is negative for tumour cells than this will be taken as evidence of non-metastatic disease. If, however, the CSF is positive by lumbar puncture before 15 days then the lumbar puncture will be required to be repeated at 15 days or beyond to determine M1 status.

Involvement of CSF pathways by tumour is defined as the unequivocal identification of primitive neuroectodermal cells, either on cytological grounds or with a combination of cytological and immunocytochemical features (e.g. reactivity for GFAP or a neuronal marker, such as synaptophysin).

d) Full neurological examination for neurosurgical evaluation, endocrine status and HUI, SDQ and OoL questionnaires.

To be performed after registration/randomisation and before the start of radiotherapy.

Information concerning premorbid health status and development, birthweight and parental heights, timing of puberty/menarche (where applicable) will be recorded at this time point.

- e) Audiology Pure Tone Audiometry if possible.
- f) Full blood count.
- g) Blood biochemistry electrolytes (ionogram), urea, creatinine, ALT, AST, Alkaline phosphatase, bilirubin, albumin, magnesium, calcium, phosphate).
- h) Endocrine status: Weight, standing and sitting height, Pubertal staging (Tanner), blood hormone concentrations (see Appendix M).

The PNET 4 treatment (e.g. the use of CCNU and scatter doses of radiotherapy) has the potential to affect subsequent fertility especially in males. Treating clinicians are encouraged to consider and discus this issue with patients/parents and to undertake fertility conservation measures (e.g. sperm storage) in appropriate individuals.

### 7. STUDY ENTRY and RANDOMISATION

Randomisation will be stratified for each country or group of countries and will be undertaken separately in each national data centre i.e. CRCTU, HIT, Italy, Nordic countries and SFOP. Further stratification will be by the presence or absence of residual tumour after surgery and by sex. Blocked randomisation will be balanced, using tables of random numbers, in order to ensure that there are equal numbers of patients in each treatment group (50% in each arm) at the end of the inclusion period. Block size may vary from one country to another, but will be a function of the number of patients to be included in the trial.

- > Randomisation is Mandatory for Entry into the Study.
- > Randomisation must be performed within 28 days following surgery.
- ➤ Registration will only be permitted following confirmation of LREC approval to be sent to the CRCTU.
- > Registration and Randomisation into the study will be conducted at the CRCTU by Faxed Registration Form:

### **CRCTU Trial Co-ordinator: TBA**

Children's Cancer Trials Team
Cancer Research UK Clinical Trials Unit (CRCTU)
School of Cancer Sciences
University of Birmingham
[name]

[contact]

[contact]

Office Hours: Monday - Friday 0900-1700

• The Registration/Randomisation Form will confirm eligibility (section 5.1) and exclusion (section 5.2) criteria.

Upon receipt of the Registration/Randomisation Form the CRCTU will return the Form by Fax within 1 working day.

- The returned form will:
  - 1) Confirm suitability for entry into the study

- 2) Assign a Study Number to the patient
- 3) Assign the Randomised Radiotherapy to be Administered –

Standard Fractionation Radiotherapy or Hyperfractionated Radiotherapy

All National Data Centres will send a copy of the Registration/Randomisation Form to the International Data by Fax within 24 hours.

For an eligible patient who is not randomised/entered into PNET 4 due to patient, parent or physician choice, the UKCCSG Brain Tumour Group recommend that the patient receives treatment with the standard arm of PNET 4 i.e. Once daily radiotherapy (23.4 Gy craniospinal dose) with weekly vincristine followed by eight planned courses of CCNU, cisplatin and vincristine chemotherapy. This recommendation applies for carefully staged Standard Risk patients as defined in the PNET 4 protocol.

Trial data will not be collected on patients not randomised/entered into PNET 4.

# **Consent for Biological Studies**

Biological studies are a fundamental part of the PNET 4 Trial. An important secondary aim of this study is to study a number of biological variables in order to determine prognostic factors in medulloblastoma and to enable subsequent stratification of patients according to biological risk groupings.

It is considered mandatory that all patients/families of patients entered into this trial will be approached to consent for collection and banking of tumour specimens. Consent for biological studies will be obtained using the same consent form as that for entry in the study.

It still strongly recommended that consent also be obtained for banking of tumour specimens under the general CCLG scheme for tumour banking - 98 BS 05 (MREC/98/04/023). This is to allow future biological studies not included in the PNET 4 study to be performed.

### 8. RADIOTHERAPY PHASE

All patients receive radiotherapy (RT) to the craniospinal axis (CSRT). This will be followed by RT to the posterior fossa. In the HFRT arm there will be a final phase of RT directed at the tumour bed.

Before the start of radiotherapy, the treating radiotherapist is strongly recommended to study the radiotherapy data forms to become familiar with the data that is to be recorded, with particular respect to target volumes and critical organs.

# 8.1 Timing of Radiotherapy (RT)

Following definitive surgery - patients should if possible begin RT within 40 days and preferably within 28 days.

Participating institutions should ensure that patients randomised to HFRT will not require a greater time to start of RT as compared to those patients receiving conventionally fractionated RT.

# 8.2 Equipment

Modality: Photon RT from a linear accelerator shall be used for the cranial (whole brain) fields and generally for the spinal fields. The use of electron spinal fields will be acceptable provided a beam of sufficient energy is available to ensure adequate irradiation of the target volume allowing for tissue heterogeneity and the junction between the photon cranial fields and spinal electron field can be precisely calculated and implemented.

### THE USE OF COBALT IRRADIATION IS UNACCEPTABLE

It is essential that within each treating centre the choice of modality for spinal treatment is standard for each arm of the trial. For example, electron fields must not be used for patients in the conventional arm of the trial if, for logistic reasons, they cannot be used in the hyperfractionated arm.

# 8.3 Energy

The cranial (whole brain) fields shall be treated with megavoltage photons with energies in the range of 4-6 MV. Energies more than 6 MV should be avoided because of under-dosage to the lateral meninges due to dose built up effect. The posterior fossa and tumour bed RT will usually be given with a higher energy. Photons of energy 4-6 MV will generally be used for spinal irradiation but electrons of suitable energy can be used as an alternative.

### 8.4 Position for treatment

Patients should be immobilised using an immobilisation system according to local practice. The patient should be maintained in the same position for the cranial and spinal components of CSRT for the duration of this treatment phase.

### 8.5 Simulator

Planning CT is strongly recommended for definition of the target volume for the craniospinal axis, posterior fossa and tumour bed volumes. It is recommended that the CT slice thickness should be no greater than 0.5 cm in the region of the cribriform fossa, base of skull, posterior fossa and craniocervical field junction, and no greater than 1.0 cm elsewhere within the craniospinal axis.

The following target volumes will be outlined:

Craniospinal axis

Posterior fossa

Tumour bed (for the final phase in the HFRT arm)

The following Organs At Risk (OARs) will be outlined:

Eye lenses, optic nerves, pituitary, inner ear, optic chiasm, brain stem, thyroid gland.

For details – see radiotherapy data forms.

Dose Volume Histograms (DVHs), if available should be constructed for the planning target volumes (PTVs) and OARs.

If the spinal field is treated with electron beams the dose along the entire spinal axis should be calculated with an appropriate correction for tissue heterogeneity.

If CT planning is not available then conventional planning of the target volumes is acceptable. Planning CT exam is strongly recommended, particularly for the posterior fossa and tumour bed target volumes.

# 8.6 Three-dimensional planning

It is strongly recommended that 3-D planning should be used to determine the target volume for posterior fossa and tumour bed. Some centres may wish to consider 3-D planning for determination of CSRT target volume.

### 8.7 Treatment volume anatomical description and dose

### 8.7.1 Target Volume

# **Craniospinal Axis:**

The Clinical Target Volume (CTV) for CSRT comprises the whole brain as well as the spinal cord and thecal sac.

#### Whole Brain Volume

The whole brain CTV should extend anteriorly to include the entire frontal lobe and cribriform plate region. In order to include the cribriform fossa within the CTV, and allowing an additional appropriate margin for PTV, the edge of the field (i.e. the geometric edge of the shielding block) would in many cases include the lenses. Previous studies from SFOP have demonstrated that provided the edge of the shielding block is at least 0.5 cm below the cribriform fossa an increased risk of frontal recurrence has not been observed. Thus the geometric edge of the shield on the film should extend at least 0.5 cm inferiorly below the cribriform plate and at least 1 cm elsewhere below the base of the skull (paying particular attention to the margin around the inferior aspect of the temporal lobes). The margin between the shielding and the anterior border of the upper cervical vertebrae should be 0.5 cm. The lower border of the cranial fields should form a precise match with the upper border of the spinal field.

### **Cervical Spinal Volume**

As much as possible of the cervical spinal volume is included in the lateral cranial fields with the junction between the cranial and spinal fields kept as inferior as possible. This is advised for two reasons:

- Avoidance of as much thyroid tissue irradiation as possible, by shielding this within the cranial volume.
- To minimise the risk of the junction being close to the primary tumour and thus the risk of a 'cold spot' in this region.

The spinal field should extend superiorly to form an accurate match with the border with the lower borders of the cranial fields.

### **Dorso-Lumbar Spine Volume**

The inferior limit of the spinal CTV must be determined by imaging the lower limit of the thecal sac on a spinal MR and will usually extend inferiorly to at least the lower border of the second sacral vertebra.

### Width of the Spinal Volume

The aim is to include the entire subarachnoid space including the extensions along the nerve roots as far as the intervertebral foramena. The spinal CTV should extend laterally to cover the intervertebral foramina. An additional margin, generally 1.0 cm on either side should be added for PTV, and an appropriate field width chosen to allow for this. The use of a 'spade' shaped field to treat the lumbo-sacral spine is not recommended.

### **Posterior Fossa Volume**

It is strongly recommended that the CTV for the posterior fossa should be determined on a planning CT. This volume encompasses the entire posterior fossa for the conventional arm (total dose 55.8 Gy) and until 60 Gy in the HFRT arm. The CTV should encompass the following:

- Superiorly the tentorium
- Inferiorly the extension of the spinal meninges 2 cm below the lower limit of the tumour as defined on the pre-operative scan. The resulting inferior field edge should at least include the outer table of the skull at the foramen magnum with a safety

margin of 1 cm to assure a reliable coverage of the entire posterior fossa meninges.

- Anteriorly 1.5 cm anterior to the limit of the tumour on a pre-operative MR.

  This will facilitate the use of posterior oblique fields to reduce the RT dose to the middle ear.
- Posteriorly the posterior extension of the meninges as far as the inner table of the skull.

  The CTV should include any herniation of the meninges through the craniotomy defect.
- Laterally the lateral extension of the meninges around the cerebellum

For PTV, an additional margin should be allowed according to departmental policy. This will generally be a margin of 0.5 cm.

A field arrangement using posterior oblique fields is strongly recommended. The purpose of this is to minimise the RT dose to the middle ears.

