## Conventionally fractionated RT (standard arm)

Craniospinal axis: 23.4 Gy in 13 daily fractions of 1.8 Gy

Post fossa: 54 Gy in 31 fractions of 1.8 Gy

Table 1.

Equivalent doses (at 1.8 Gy per fraction) for HFRT in PNET-4

		CNS Late effects Equivalent Dose	Anti-tumour effect Equivalent Dose
		$\alpha/\beta=2$	$\alpha/\beta = 10$
	36 Gy	28.42	33.56
CSRT	36 Gy 36 fractions		
Post Fossa	60 Gy	47.37	55.93
	60 fractions		
Tumour bed	68 Gy	53.68	63.39
	68 fractions		

Thus hyperfractionation has the potential for preferentially increasing the anti-tumour effect without an equivalent increase in CNS late effects.

The dose-response relationship for medulloblastoma is well known and it seems that increasing the dose without increasing the late effects on CNS tissue might additionally improve local and regional tumour control  $28\ 40\ 41\ 42$ .

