### 8.7.4 Total Treatment Dose

# **Standard RT Regimen**

Brain – 23.40 Gy in 13 daily fractions of 1.80 Gy Spine - 23.40 Gy in 13 daily fractions of 1.80 Gy Primary tumour boost – 30.6 Gy in 17 daily fractions of 1.80 Gy Total dose to primary – 54 Gy in 30 daily fractions of 1.80 Gy

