### The minimum time interval between fractions will be 8 hours

The dose per fraction will be 1.80 Gy in the conventional RT arm and 1.00 Gy in the HFRT arm.

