30.6 Gy in 17 fractions of 1.8 Gy

# **Hyperfractionated RT (HFRT)**

1 Gy b.d. (minimum interval between fractions 8 hours). 10 fractions per week

Craniospinal axis:

36 Gy in 36 fractions of 1 Gy

Posterior fossa:

24 Gy in 24 fractions of 1 Gy

Tumour Bed:

8 Gy in 8 fractions of 1 Gy

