### 13.9 Per protocol analysis

A per protocol analysis will also be carried out to study stability of results, but confirmatory conclusions will depend on the Intention to Treat analysis.

[figure not shown]
The per protocol analysis will exclude patients who have been randomised but who do not meet the eligibility criteria e.g. age, histology, staging, other malignant tumour disease etc. In addition, this analysis will exclude patients who do not meet eligibility criteria after central review (pathological, radiological and radiotherapy review) and patients who are not reviewed. Patients will also be excluded from per protocol analysis for the following reasons: patients who, do not receive any treatment at all, start RT more than 40 days after definitive surgery, do not meet RT quality assurance because of major deviations on RT treatment chart, receive less than 75% of the intended RT arm and thereafter are switched to the other arm, receive less than 90% of intended RT dose and patients who receive less than 4 cycles of chemotherapy with less than 80% of doses applied in each cycle. In the per

protocol analysis, if a patient is allocated to one arm and receives the other arm as treatment, analysis will be according to the treatment actually given.

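### The standard-arm posterior fossa dose is stated inconsistently: 54 Gy in 30 fractions, 54 Gy in 31 fractions, and 55.8 Gy

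*Protocol*

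**What the plan says.** The protocol describes the standard-arm treatment of the posterior fossa in several places.

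- Section 2 (Synopsis): 54 Gy, with no number of fractions.
- Section 4.4.2, in the list of doses for each arm: "Craniospinal axis: 23.4 Gy in 13 daily fractions of 1.8 Gy", then "Post fossa: 54 Gy in 31 fractions of 1.8 Gy".
- Section 8.7.1, Posterior Fossa Volume: the clinical target volume covers "the entire posterior fossa for the conventional arm (total dose 55.8 Gy".
- Section 8.7.4, Standard RT Regimen: "Primary tumour boost – 30.6 Gy in 17 daily fractions of 1.80 Gy", and a total to the primary of "54 Gy in 30 daily fractions of 1.80 Gy".
- Section 8.7.4, Standard Fractionation Regimen: 23.4 Gy in 13 fractions to the craniospinal axis, then "30.6 Gy in 17 fractions of 1.8 Gy" to the posterior fossa.

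Section 8.7.4 also fixes the fraction size: "The dose per fraction will be 1.80 Gy in the conventional RT arm and 1.00 Gy in the HFRT arm".

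Section 13.9 makes the intended dose an analysis criterion. The per-protocol analysis leaves out patients who "receive less than 90% of intended RT dose", and those who receive under 75% of the allocated radiotherapy and then change arm.

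**The concern.** All these statements are current text about this trial's own control arm. None comes from the amendment log or describes another study, and they cannot all be true. Neither Amendment 1 nor Amendment 2 reports a change to this dose, and no section gives one statement precedence.

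Two things are at stake. The first is uniformity of the control treatment: a centre working from section 8.7.1 and one working from section 8.7.4 would read different totals. Routine checking need not catch this. Under section 8.8, quality control is mandatory for the craniospinal part, but for the posterior fossa only after a posterior fossa relapse. National groups also translate the protocol literally (Appendix B), so an inconsistency would be carried into each translation. The second is the per-protocol analysis, whose dose limits are percentages of an intended dose that has two values.

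The ambiguity falls on one arm. The hyperfractionated totals agree wherever they appear, so randomisation does not balance it.

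**Working it through.** Inputs, all from the protocol: 1.8 Gy per fraction (section 8.7.4); craniospinal part 13 fractions (sections 4.4.2 and 8.7.4); posterior fossa part 17 fractions (section 8.7.4); stated totals 54 Gy (sections 2, 4.4.2 and 8.7.4) and 55.8 Gy (section 8.7.1); stated fraction numbers 30 (section 8.7.4) and 31 (section 4.4.2).

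Formula: total dose = number of fractions x dose per fraction.

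1. Section 8.7.4 reproduces. 13 x 1.8 = 23.4 Gy and 17 x 1.8 = 30.6 Gy. The sum is 54.0 Gy in 13 + 17 = 30 fractions, and 30 x 1.8 = 54.0 Gy.
2. Section 4.4.2 does not. 31 x 1.8 = 55.8 Gy, not 54 Gy. To reach 54 Gy in 31 fractions the fraction would have to be 54/31 = 1.74 Gy, against the stated 1.8 Gy.
3. Section 8.7.1 matches the fraction count of section 4.4.2 but not its total. 55.8/1.8 = 31 fractions, one more than section 8.7.4.
4. Size of the gap: 55.8 - 54 = 1.8 Gy, and 1.8/54 = 3.3%.
5. Hyperfractionated arm, for comparison: 36 + 24 = 60 Gy to the posterior fossa and 60 + 8 = 68 Gy to the tumour bed. These agree in sections 4.4.2, 8.7.1 and 8.7.4.

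Effect on the section 13.9 rules, assuming they are applied to the total posterior fossa dose (the section does not name the volume):

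- 90% rule: 0.90 x 54 = 48.6 Gy (27 fractions); 0.90 x 55.8 = 50.22 Gy (27.9, so 28 whole fractions).
- A control patient given 27 fractions has 48.6 Gy. That is 48.6/54 = 90.0%, not below the limit, so kept; or 48.6/55.8 = 87.1%, so excluded.
- With 28 fractions (50.4 Gy) the patient is kept on either reading, since 50.4/55.8 = 90.3%. With 26 (46.8 Gy) the patient is excluded on either, since 46.8/54 = 86.7%. Only 27 fractions gives a different answer.
- A patient given the full 54 Gy is at 54/55.8 = 96.8% of the higher figure, so is not excluded on either reading.
- 75% arm-switch rule: 0.75 x 54 = 40.5 Gy; 0.75 x 55.8 = 41.85 Gy.

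**The case against.** The best defence is that the dose is defined where a reader would look for it. Section 8.7.4 is the dedicated dose section, its components add up, and the synopsis agrees. Section 4.4.2 is rationale and also states 54 Gy; only its fraction number conflicts. The 55.8 Gy total appears once for this trial, in a parenthesis in a section on anatomical volume. This stands as a description: two outlying statements against a consistent set. It does not remove the conflict, because section 8.7.1 is a working instruction and nothing ranks the sections. Nor does it show which figure is right.

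A reader might infer more than the document supports.

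- That patients received different doses, or were harmed. No section shows this. The text is version 3.0 of July 2010, section 13.10 planned recruitment to the end of 2005 (with prolongation foreseen in section 13.1), and section 4.7.3.1 already cites a comparison of event-free survival by arm. Radiotherapy may have been largely complete. Section 7 still describes registration, however, and closure is not stated.
- That all twelve countries listed in section 13.10 were exposed. Appendix B says HIT Group centres use the HIT 2000 protocol with amendments, which is not at hand.
- That the biological contrast between the arms shifts by a calculable amount. The section 4.4.2 formula, at 2 Gy per fraction and alpha/beta 2, gives 54 x 3.8/4 = 51.3 Gy, whereas Table 3 prints 48.9 Gy for the same dose. A comparison with the tumour bed also leaves out the rest of the posterior fossa. No such figure is relied on here.
- That the 55.8 Gy in Table 3 supports section 8.7.1. That row describes a cited earlier regimen.

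**Conclusion.** The protocol is wrong as written on this point. Current text gives two totals and two fraction numbers for one control treatment, and one of the statements contradicts itself. The size is one fraction, 1.8 Gy or 3.3%, in the standard arm only.

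The statistical consequence is narrow. It is confined to the per-protocol set, where the 90% limit gives different answers only for a control patient who stops at 27 fractions, and the 75% limit moves by 1.35 Gy (41.85 - 40.5). Section 13.9 treats that analysis as a check of stability and bases confirmatory conclusions on intention to treat. A reader might infer that the primary comparison is compromised. It is not: the event-free survival test, its significance levels and the power calculation do not use the radiotherapy dose.

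The point must be fixed because a control prescription in a radiotherapy trial should have one reading, not because harm or bias has been shown. It rests on the quoted text alone. The per-protocol figures add one assumption, that the rules refer to the total posterior fossa dose.

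**What to change.** - The study committee should reconcile sections 4.4.2 and 8.7.1 with sections 2 and 8.7.4, so that total dose, number of fractions and dose per fraction agree throughout. Which figure is right is for the committee.
- Section 13.9 should state the single intended dose, and the volume it refers to, for the 90% and 75% rules.
- Any centre still treating patients should be told of the correction, and national translations checked.
- The report should describe the delivered standard-arm dose by country, where it was recorded. The protocol names a radiotherapy data form (Form 7, Appendix Q) but does not show its fields, so availability must be confirmed first.

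The cost is a short amendment and a notice to centres. Describing delivered dose adds a table if the data exist. The sample size and the primary analysis do not change.
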